The tooth/teeth site(s) will be prepared utilizing a papilla-sparing, sulcular incision extending one tooth mesial and distal to the tooth/teeth site(s) to be treated and split-thickness flap elevated on buccal aspect leaving a thin periosteum as recipient bed. Extension of the flap apically and laterally to allow for adequate coronal advancement and coverage of the ADM graft material will be insured. Mesio-distal and apico-coronal dimensions will be measured at recipient site the ADM material trimmed after hydration and washing per package instruction to equal dimensions and uniform thickness will be performed. Exact AMD graft dimensions will be measured with a calibrated UNC-15 periodontal probe and its thickness will be measured using a caliper prior to placement within the suprapariosteal pouch at the recipient site. ADM graft will be secured in position and overlying flap secured in a coronal position with multiple suture techniques.

Table 2: Tunneling and ADM technique

	
Pt. presents with Miller Class II and III recession defects.

---	---

	
Incision made on the front of each tooth to be treated.

	
Elevation of the flap with blunt dissection to necessary level.

	
Insertion of acellular dermal matrix.¹⁵

	
Positioning of acellular dermal matrix with sutures overlying root surfaces.

	
Flap positioned at the desired level and sutured into place.

	
One month post-operative evaluation of healing.

To help guard against possible infection, a pre-surgical antibiotic loading dose will be dispensed and prescriptions for relief of post-surgical discomfort, follow-up antibiotics and written home care instructions will be provided.

Follow up visits: The surgical sites will be examined at 1 week (visit 2) and 2 weeks (visit 3) after surgical visits and loose sutures will be removed. Exams will then be scheduled at 1 month (visit 4), 3 months (visit 5), 6 months (visit 6), and 1 year (visit 7).

During these follow up visits the following will take place:

1. Medical history review (all visits)
2. Assess for adverse events experience (all visits)
3. Intra-oral photographs: (all visits)
4. Clinical measurements:

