The width of keratinized tissue (KT) will be assessed at visits 4, 5, 6 and 7. Tissue thickness (TT1 and TT2) will be evaluated at visits 5, 6 and 7. Clinical measurements will be collected by calibrated examiners. Measurements from all visits will be compared to baseline in order to evaluate the progression of healing over time up to 12 months post-op.
5. Patient satisfaction survey
This survey will be performed at visits 2 and 4 using a visual analogue scale (VAS) based questionnaire regarding esthetic appearance, pain, swelling, bruising, effects on daily activities. Esthetic evaluation by the patient will also be assessed at visits 6 and 7.
6. Pink Esthetics Score (PES)
This standardized assessment of esthetics will be performed at visits 6 and 7 by blinded, calibrated examiners.
7. Study participation and satisfaction survey to be completed at final study visit (visit 7)

Inclusion/Exclusion Criteria:

Inclusion Criteria	Exclusion Criteria
English speaking	Non-English speaking
At least 18 years old	Less than 18 years old
Must be a patient of the UAB Dental School	Smokers/tobacco users (>10 cigarettes/day)
Able to read and understand informed consent document.	Patients with systemic pathologies or conditions contraindicating oral surgical procedures or adversely affecting wound healing.
One or more adjacent teeth (up to four) with Miller class I or II gingival recession defects and ≤ 2mm of KT at each site to be treated.	Presence of active periodontal disease or radiographic interproximal bone loss or tooth malposition, which would yield a Miller class III or IV categorization for the recession defect.
Presence of periodontally healthy, non-carious neighboring teeth, healthy implants, or edentulous ridges on either side of the involved site(s)	Presence of frenulae or other soft tissue anomalies at the site(s) to be treated that, in the opinion of the investigators, will interfere with successful access and treatment of the soft tissue defects.
No anticipated need for restorative care at the teeth to be treated during the study period.	Previous soft tissue grafting at the site(s) to be treated

--	--

Group Table:

Group	Treatment	Number of participants
Group 1	Vestibular incision suprapariosteal tunnel access (VISTA) + Acellular Dermal Matrix (ADM) graft	20
Group 2	Sulcular tunnel access + Acellular Dermal Matrix (ADM) graft	20

3. Study Background:

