- Group sample sizes of 20 and 20 achieve 92% power to detect non-inferiority using a one-sided, two-sample t-test. The margin of non-inferiority is -1.0. The true difference between the means is assumed to be 0.1. The significance level (alpha) of the test is 0.025. The data are drawn from populations with standard deviations of 1.0 and 1.0.

- Regarding patient-centered outcomes, there is not adequate data available to complete an accurate sample size analysis to determine the proper N, therefore in this respect this study serves as a pilot study.

5. Benefits:

Benefits of this project for individual participants include enhancing periodontal soft tissue health and thus decreasing the risks of dentinal sensitivity, radicular (root) caries (tooth decay), and tooth root structure wear as well as a reduction in progressive recession and periodontal attachment loss at the tooth sites to be treated. Information gained from this research may be used by investigators to facilitate a healthier environment around teeth with gingival recession and a lack of keratinized tissue (KT) with therapies that are well-accepted with low post-operative morbidity.

6. Risks

The only risks associated with this protocol involve potential loss of confidentiality and randomization. Precautions will be taken to ensure that patient confidentiality is maintained. All records will be assigned identifying alphanumeric codes and the list linking identifying PHI to patient data will be kept on a password protected computer and destroyed immediately after statistical analysis is completed. All surveys and consent documents will have assigned non-identifying, alphanumeric codes and the list linking personal information and patient data will be kept on a password protected computer and destroyed immediately after data analysis have been completed. Intra-oral photos will also be assigned alphanumeric codes that link with codes assigned to the demographic data collection form and consent documents. Photos will be stored as digital images on encrypted computers in the department of Periodontology. The photos will be used in the publication and presentations.

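### The plan has no exit assessment and no rule for missing 6- or 12-month outcomes, so by default the 12-month comparison of KT and tissue thickness rests on visit 7 attenders, although earlier values are already collected

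*Combined protocol and SAP*

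**What the plan says.** All references are to the combined protocol and SAP.

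- **Schedule (Section 2, Follow up visits).** Exams fall at 1 and 2 weeks (visits 2 and 3) and at 1, 3, 6 and 12 months (visits 4 to 7). No early-exit or withdrawal visit is listed.
- **Repeated measures (item 4).** "The width of keratinized tissue (KT) will be assessed at visits 4, 5, 6 and 7". TT is measured at visits 5, 6 and 7. The item adds that every visit's measurements will be set against baseline to follow healing, but names no model.
- **Patient ratings (items 5 and 7).** The VAS satisfaction survey is given at visits 2 and 4. The patient's esthetic rating is repeated at visits 6 and 7. A separate item reads "Study participation and satisfaction survey to be completed at final study visit (visit 7").
- **Outcomes (Section 4).** Root coverage, KT, TT, the pink esthetic score (PES) and patient-assessed esthetics are judged at 6 and 12 months. The item 7 survey is not on this list.
- **Test (Section 4, sample size bullet).** "Group sample sizes of 20 and 20 achieve 92% power to detect non-inferiority using a one-sided, two-sample t-test". The bullet names no endpoint, unit or time point.

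No analysis set, missing-data rule or dropout allowance appears. The 40 patients to be recruited are exactly the 20 + 20 in the power statement.

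**The concern.** The trial follows patients for a year, and nothing says what happens to the comparison when one of them stops attending. A two-sample t-test at 12 months needs a visit 7 value, so a patient last seen at month 6 drops out of it by default. That patient's KT at visits 4 to 6 and TT at visits 5 and 6 will have been recorded, but no rule brings them into the between-group comparison.

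If patients with a disappointing graft are more likely to leave, and more of them leave one arm, the completers' means flatter that arm. In a non-inferiority comparison this pushes towards a false positive conclusion. The same patients would never answer the item 7 survey, and would give no esthetic rating after month 1 unless they reached visit 6.

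**Working it through.** **1. The plan's own figure.** Inputs from the sample size bullet in Section 4: 20 per arm; SD 1.0 in both arms; one-sided alpha 0.025; an expected difference of +0.1; and, for the margin, "The margin of non-inferiority is -1.0".

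Noncentrality = (0.1 + 1.0) / (1.0 × √(1/20 + 1/20)) = 1.1 / 0.3162 = 3.479, with 38 degrees of freedom. One-sided power at 0.025 is 92.4%, so the stated 92% reproduces. It requires all 40 patients to have a value.

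**2. Non-selective loss, equal in both arms (assumed rates).** Noncentrality = 1.1 / √(2/n).

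| Loss | n per arm | Noncentrality | Power, completers only |
|---|---|---|---|
| 10% | 18 | 3.300 | 89.4% |
| 20% | 16 | 3.111 | 85.3% |
| 30% | 14 | 2.910 | 80.0% |

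**3. Selective loss from the worse arm only.** Assumptions: the SD and margin above apply to KT; the true difference sits at the margin, −1.0; the correlation ρ between 6- and 12-month values is 0.6 to 0.8; the k lowest of 20 at 6 months in the worse arm miss visit 7; nobody leaves the other arm.

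If a fraction q leaves, the completers' mean in that arm shifts by about ρ × φ(z_q) / (1 − q), where φ is the standard normal density and z_q the q-quantile. For q = 0.20 the ratio is 0.350. The shift is then 0.6 × 0.350 = 0.21 to 0.8 × 0.350 = 0.28, and the difference becomes about −0.79 to −0.72. Simulation with 20,000 trials per setting gives slightly smaller shifts at this sample size:

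| k of 20 | Completers' difference, ρ 0.6 to 0.8 | False non-inferiority, ρ = 0.6 | ρ = 0.8 |
|---|---|---|---|
| 2 | −0.89 to −0.86 | 5.5% | 7.0% |
| 3 | −0.84 to −0.79 | 7.4% | 10.0% |
| 4 | −0.80 to −0.74 | 8.8% | 13.4% |

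An independent rerun gave 5.8, 7.2 and 8.8% at ρ = 0.6, and 7.2, 10.0 and 13.1% at ρ = 0.8. The nominal rate is 2.5%.

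**4. Other mechanisms, same margin and SD.**

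| Mechanism | Completers' difference | False non-inferiority |
|---|---|---|
| Same k lowest lost in both arms, ρ 0.6 to 0.8 | about −1.00 | 2.9% to 3.7% over two runs |
| k lost in worse arm, k − 1 in the other, ρ 0.6 to 0.8 | −0.96 to −0.93 | 3.7% to 5.2% |
| Worse arm only, below-median patients twice as likely to leave, ρ 0.6 to 0.8 | −0.98 to −0.95 | 2.8% to 3.4% |
| Worse arm only, k lowest lost, ρ = 0.3 | not tabulated | 3.8% to 4.5% |

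In the first row the difference is unbiased. The small excess arises because trimming the low values makes the t-test's standard error slightly too small. In the other direction, losing the lowest 6 of 20 from the worse arm at ρ = 0.7 gives 16.1%.

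**5. Using the 6-month value.** In the six settings of step 3, a likelihood estimate that includes the 6-month value returns −1.00, with a false non-inferiority rate of 2.4% to 2.8%. It also recovers precision. With 20% missing, the variance of an arm mean is inflated by 1 / (1 − 0.2) = 1.25 among completers. With the 6-month value at ρ = 0.8 the factor is 1 + 0.25 × (1 − 0.64) = 1.09.

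**The case against.** The strongest reply is that the plan is silent about leavers and does not exclude them. The t-test appears only in a sample size bullet with no endpoint or time point, and item 4 gives the interim measurements a use. A reader might infer that the protocol prescribes a completers-only analysis and discards the earlier data. The documents do not say so. What stands is that completers-only is the default the plan leaves open, and that comparing each visit with baseline does not say how a leaver counts between arms.

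A reader might also infer that satisfaction as a whole is lost for leavers. It is not: the VAS survey at visits 2 and 4 is complete for anyone who attends through month 1. Only the item 7 survey depends on visit 7, and it is not a Section 4 outcome.

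Nor is bias at 6 months shown. The simulated leavers all attend visit 6, so that comparison loses nobody in these calculations.

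The 5-13% range needs the very poorest patients to leave one arm only. Disappointed patients may leave both arms, and step 4 shows that milder mechanisms cost much less. That the likelihood estimate returns −1.00 follows from letting dropout depend only on the observed 6-month value. Both criticisms stand and limit the size of the point, but they do not supply the missing rule.

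The model recommended here covers only KT and TT. PES has no scheduled score before visit 6, and no root-coverage measurement is listed among the follow-up measurements. The trial is titled a pilot, but it also states a powered non-inferiority test.

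**Conclusion.** The point holds as a gap with a better method readily available. There is no exit assessment, no rule for missing 6- or 12-month outcomes, and no rule that brings earlier KT and TT values into the 12-month between-group comparison.

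For 2 to 4 losses in 20, the effect on false non-inferiority runs from about 3-4% when both arms lose alike to about 5-13% when only the worse arm loses its poorest patients; the second is an upper scenario. Dropout rate, direction, correlation and the application of the margin to KT are all assumptions, because the documents give none of them. The change should be made, but the documents do not show that the result will be biased.

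**What to change.** 1. In Section 4, state that KT and TT at 12 months will be compared with a likelihood-based repeated-measures model using all scheduled visits (KT visits 4 to 7, TT visits 5 to 7), for all randomised patients in their randomised arm, in place of a t-test on visit 7 attenders.
2. In Section 2, state that a patient who withdraws will be given the item 7 survey and the patient esthetic rating at the last visit attended, or by phone or mail. Report these as early-exit values with their timing, separate from the 12-month ratings.

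The cost is a paragraph in Section 4, a sentence under Follow up visits, and perhaps one or two surveys by phone or mail. No new visits, staff or procedures are needed. There are two limits: the model relies on dropout depending on observed values, and exit ratings describe a time earlier than 12 months.

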A prospective, randomized clinical trial to compare vestibular incision supraperiosteal tunnel access (VISTA) and sulcular tunnel access root coverage procedures with coronally advanced flap and acellular dermal matrix (ADM) to treat teeth with gingival recession and lack of adequate keratinized tissue. A pilot study.

Study Protocol & Statistical Analysis Plan

NCT03566108

August 31, 2022

[name], MS, Principal Investigator

University of Alabama at Birmingham
Birmingham, AL 35294

A prospective, randomized clinical trial to compare vestibular incision suprapariosteal tunnel access (VISTA) and sulcular tunnel access root coverage procedures with coronally advanced flap and acellular dermal matrix (ADM) to treat teeth with gingival recession and lack of adequate keratinized tissue. A pilot study.

1. Study Protocol 1. Objectives/Specific Aims:

This investigator-initiated study will compare two commonly used soft tissue grafting techniques [vestibular incision suprapariosteal tunnel access (VISTA) vs. sulcular tunnel access root coverage procedures with the uses of acellular dermal matrix (ADM)] to achieve coronal flap advancement and root coverage as well as augmentation of soft tissue at intraoral tooth sites. Research data and daily clinical observations reveal that teeth with gingival recession and a lack of adequate keratinized tissue (KT) are more prone to persistent gingival inflammation, dentinal sensitivity, radicular (root) caries (tooth decay), faster periodontal attachment loss, and compromised plaque control. Soft tissue grafting (by various techniques) aims at changing the quality, quantity and placement of the soft tissue around teeth by covering exposed root surfaces and creating or increasing the zone of keratinized mucosa (KM) surrounding the affected teeth. Both techniques tested have shown good clinical outcomes with regard to root coverage, but clinical reports of the VISTA technique and other similar techniques suggest that patients experience a decrease in site morbidity and discomfort post-operatively. To our knowledge, these 2 types of grafting techniques have not been compared in a prospective trial for differences in clinical (percentage of root coverage, amount of KT increase, tissue thickness increase, and practitioner-assessed esthetics) and patient-centered outcomes (pain, swelling, change in daily activities, and patient-assessed esthetics) in a controlled study.

2. Materials and Method:

Study population:

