- Gingival Index (*GI*, Loe and Silness) at surgical site(s). A periodontal probe will be swept around the tooth sulcus at a depth of 1-2 mm. The examiner will determine the status of tissue health. A single score will be recorded for buccal and lingual/palatal surface of each tooth examined as follows:

0 = healthy tissue

1 = mild inflammation but no bleeding

2 = moderate inflammation with bleeding

3 = severe inflammation with a tendency toward spontaneous bleeding

- Width of keratinized tissue (KT) will be measured at tooth site(s) at the mid-buccal aspect from the mucosal margin to the mucogingival junction.
- Width of attached tissue (AT) will be calculated by subtracting PD from KM
- Tissue Thickness (TT1 and TT2) at the buccal mucosa will be measured during the surgical visit by horizontal transmucosal probing (sounding the bone) using an endodontic reamer after local infiltration of anesthetic prior to surgical site preparation. TT1 and TT2 will be measured at 2 mm and 5 mm from the mucosal margin, respectively.

Clinical photographs of the tooth site (s) will be obtained with one digital SLR camera.

Randomization: two groups (Participants will be randomized like the flip of a coin to one of the two groups listed.) Randomly generated treatment groups will be printed on note cards and placed in sealed opaque envelopes. Once the patient consents to participate in the study an envelope is opened, and the patient is then offered the allocated treatment regimen.

Group 1: will receive vestibular incision supraperiosteal tunnel access (VISTA) + Acellular Dermal Matrix (ADM) graft around teeth with gingival recession and lack of KT.

Group 2: will receive sulcular tunnel access + Acellular Dermal Matrix (ADM) graft around teeth with gingival recession and lack of KT.

Surgical visit (Visit 1): Patients will be anesthetized via infiltration around recipient tooth/teeth site(s). Study surgeon will confirm measurements taken at baseline with relation to width of keratinized tissue (KT) and evaluate thickness of mucosa (TT1 and TT2) as described above. Surgeon will then measure the recipient site to determine the size of graft needed and ensure that surgical treatment will avoid any vital structures. Soft tissue grafting procedures will include local anesthesia, monitoring of vital signs (bp, HR, O2 sat). Study surgeons will follow standard-of-care procedures for soft tissue as follows:

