Soft tissue grafting for root coverage and alteration of the quality of gingival tissue surrounding teeth was originally described in 1956 using a Lateral Pedicle Flap.¹ Since that time, myriad techniques and materials have been described to improve clinical outcomes and patient acceptance.²⁻⁶ Systematic reviews and meta-analyses have concluded that root coverage and KT gain at sites with Miller class I or II defects could be reliably achieved with the use of allogeneic donor tissue as well as autogenous connective tissue harvested from a patient’s palate.⁷⁻⁹ Use of a tunnel technique has also been shown to demonstrate decreased post-operative discomfort when compared with a standard coronally advanced flap.¹⁰ Recently, there has been renewed interest in vestibular incisions, originally described in 1912¹¹, for the coronal advancement of gingival tissues with the use of graft materials due to purported decrease in post-operative discomfort and healing time.

Given the increase in the number of procedures performed, this study seeks to compare two established tunneling technique procedures with the use of allogeneic soft tissue graft materials to evaluate clinical and patient-centered outcomes to determine if there are any notable differences in post-operative healing and clinical outcomes associated with each technique.

4. Outcomes Measures

Outcomes will be measures by an evaluation of the following:

- Percentage previously visible root surface that has been covered by gingiva at 6- and 12-months following grafting with VISTA and sulcular tunnel access with ADM as compared to the baseline data.
- KT width as measured in mm by practitioner at 6- and 12-month following grafting with VISTA and sulcular tunnel access with ADM
- Change in tissue thickness evaluated with gentle intrasulcular probing and level of transparency of the grafted sites at 6 and 12 months.
- Practitioner-assessed esthetic outcomes using a standardized pink esthetic scale (PES) at 6 and 12 months postoperatively.
- Patient-assessed esthetic outcomes of root coverage and soft tissue appearance at 6 and 12 months post-operatively
- Patient centered outcomes including pain, bleeding, swelling, change in daily activities at 1 week and 1 month postoperatively, see attached Visual Analog Scale (VAS)

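### The only between-group test named is an unadjusted one-sided non-inferiority t-test, while the aim is to find differences; a patient-level KT comparison adjusted for baseline, with a two-sided 95% CI, would serve both

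*Combined protocol and SAP*

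**What the plan says.** **Aim.** Section 1 (Objectives/Specific Aims) motivates the trial by saying that "these 2 types of grafting techniques have not been compared in a prospective trial for differences in clinical" and patient-centered outcomes. Section 3 (Study Background) says the study is to "determine if there are any notable differences in post-operative healing and clinical outcomes associated with each technique".

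**Test.** The only between-group test named is in the sample-size bullet of section 4 (Outcomes Measures): "Group sample sizes of 20 and 20 achieve 92% power to detect non-inferiority using a one-sided, two-sample t-test". It continues: "The margin of non-inferiority is -1.0. The true difference between the means is assumed to be 0.1". Alpha is 0.025 and the SD is 1.0 in each group. No outcome, visit, unit, reference arm or covariate is given. The next bullet covers the patient-reported side: "Regarding patient-centered outcomes, there is not adequate data available to complete an accurate sample size analysis". In that respect it calls the study a pilot; the title calls the whole trial one.

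**Data.** Section 2 provides for a baseline KT measurement: "Study surgeon will confirm measurements taken at baseline with relation to width of keratinized tissue (KT) and evaluate thickness of mucosa (TT1 and TT2"). KT is measured again at 1, 3, 6 and 12 months, and section 4 lists KT width in mm at 6 and 12 months as an outcome. Section 2 also says that measurements will be compared with baseline to follow healing, which describes change over time and not a comparison of techniques.

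**Unit.** Patients are randomized, 20 per group. Each may contribute one to four adjacent teeth, each with KT of 2 mm or less. No rule turns several teeth into one value per patient.

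**The concern.** The question is about differences, and the one test named is built to answer something narrower. A one-sided non-inferiority result says that one technique is not worse than the other by as much as the margin. It does not estimate how far apart they are, or in which direction.

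If the trial reports only that test, a reader learns that a deficit of 1.0 has been excluded. The reader does not learn whether the techniques perform alike or the tested one is better.

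Two further features matter. Baseline KT is already collected, yet no between-group comparison uses it. And because a patient can supply up to four teeth, an analysis by tooth that ignored the patient would overstate the amount of independent information. The documents neither plan such an analysis nor exclude it.

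**Working it through.** **Inputs from section 4:** n = 20 per group, margin -1.0, true difference d = +0.1, SD 1.0, one-sided alpha 0.025. Because the SD is 1.0, differences in outcome units and in SD units coincide.

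**1. Reproduce the plan's figure.** The noncentrality is (d + 1.0)/(SD × √(2/n)) = 1.1/√0.1 = 3.479, with 38 df and critical value t = 2.024. Power from the noncentral t is 92.4%. The stated 92% is right.

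**2. How often the same test is met at other true differences (20/20).**

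| True difference | Noncentrality | Test met |
|---|---|---|
| +0.5 | 1.5/√0.1 = 4.743 | 99.6% |
| +0.1 (plan) | 3.479 | 92.4% |
| 0 | 1.0/√0.1 = 3.162 | 86.9% |
| -0.3 | 0.7/√0.1 = 2.214 | 57.8% |
| -0.5 | 0.5/√0.1 = 1.581 | 33.8% |

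The test separates a disadvantage from equality well. It separates equality from an advantage poorly.

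**3. Losses (assumed; the plan gives no allowance).** At d = +0.1, 18/18 gives 89.4% and 16/16 gives 85.3%.

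**4. What the same 40 patients say about a difference.** The unadjusted two-sided 95% half-width is 2.024 × √0.1 = 0.640 SD. Two-sided power is 34% for a difference of 0.5 SD and 6% for the plan's own +0.1; 80% power needs about 0.91 SD. So at a true +0.5 SD the non-inferiority test is met in 99.6% of trials, but the 95% CI excludes 0 in only 34%.

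**5. The interval keeps the decision.** For a given model, a one-sided 0.025 test against -1.0 passes exactly when the lower limit of the two-sided 95% CI exceeds -1.0. Simulation of the t-test gave 100% agreement. Under ANCOVA, at a true difference of -1.0 and an assumed r = 0.5, the simulated one-sided error was 2.5%.

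**6. What baseline adjustment does.** Let r be the correlation of baseline with follow-up KT. The documents give no value, so every r here is an assumption. With balanced baselines the half-width is t(37 df) × √(1 − r²) × √0.1, where t = 2.026. Chance imbalance multiplies the variance by 1 + F/38, with F distributed as F(1, 38); the last column averages the half-width over F for a normal covariate.

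| Assumed r | Balanced | Averaged over imbalance |
|---|---|---|
| 0.1 | 0.638 | 0.646 |
| 0.3 | 0.611 | 0.620 |
| 0.5 | 0.555 | 0.562 |

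The averaged half-width equals the unadjusted 0.640 at about r = 0.17. At r = 0 and a true difference of 0, non-inferiority power is 86.85% (balanced) or 85.9% (averaged over imbalance), against 86.9% unadjusted.

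**The case against.** **The bullet is a sample-size statement and does not bind the final analysis.** This stands. A reader might infer that the sponsor has committed to an unadjusted t-test, or to counting teeth as independent; the documents say neither. But no other between-group method is named, so it is the only guide to the intended comparison.

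**Non-inferiority is a legitimate way to compare two established techniques.** This also stands. A reader might infer that the test contradicts the aim. It is compatible with it, and the fix retains it.

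**The 92% is correct and labelled as power for non-inferiority.** Agreed. The documents do not present it as power to find a difference.

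**The test is not blind to differences.** A reader might infer that it is met about as easily whatever the truth. For a disadvantage, the direction it guards against, that is wrong: the rate falls to 57.8% at -0.3 and 33.8% at -0.5.

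**ANCOVA may gain little.** This is fair. Precision improves only above about r = 0.17, r is unknown, and the KT entry limit may lower it. The interval and the patient-level unit do most of the work, and neither depends on r.

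**A pilot of 40 is expected to have little power for a 0.5 SD difference.** True, and this favours presenting the result as an estimate with an interval.

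**Conclusion.** The point holds as a worthwhile, inexpensive improvement to the analysis. It is not an error in the power calculation. The one named test would exclude a disadvantage as large as 1.0, but passing it would leave open whether the techniques are equal or the tested one is better (met in 86.9% of trials at 0 and 99.6% at +0.5 SD). The stated aim needs an estimate of the difference, and the plan specifies none.

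The power figures rest on the plan's SD of 1.0 and full follow-up of 20 per group. The ANCOVA figures add assumed values of r. Reading the -1.0 margin as mm of KT width is plausible but unconfirmed. The documents do not support a claim that adjustment will raise power, or that this trial can settle differences well below about 0.9 SD.

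**What to change.** 1. **KT width.** At 6 and 12 months, with one named in advance as the main visit, take each patient's mean KT over the treated teeth. Compare groups by ANCOVA with the patient's mean baseline KT as covariate. Report VISTA minus sulcular tunnel with a two-sided 95% CI.
2. **Non-inferiority reading.** Have the sponsor state the outcome, unit, visit and reference arm behind the -1.0 margin. If these are KT width in mm and sulcular tunnel as reference, judge the lower limit against -1.0; the one-sided level stays 0.025. Present the whole interval as estimation that may be inconclusive.
3. **Power statement.** Beside the 92%, say that it assumes a +0.1 advantage and full follow-up, and give 86.9% for a true difference of 0. Print no adjusted power as expected.
4. **Tissue thickness.** Use the same approach only once the two descriptions are reconciled. Section 2 says it "will be measured during the surgical visit by horizontal transmucosal probing (sounding the bone) using an endodontic reamer"; section 4 has "Change in tissue thickness evaluated with gentle intrasulcular probing and level of transparency of the grafted sites at 6 and 12 months". Until then, a baseline on the same scale may not exist.
5. **Other outcomes (reporting suggestion only).** Give patient-level differences with 95% CIs. First reconcile the VAS items (bruising in section 2, bleeding in section 4) and state where the root-coverage measurement comes from, since the clinical parameters in section 2 list no recession depth.

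**Cost.** For KT: SAP wording and a standard model, with no added patients, visits or measurements. The covariate uses one degree of freedom: under 0.1 point of power with balanced baselines, and about 1 point (86.9% to 85.9%) averaged over chance imbalance if baseline KT is uninformative.

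### Does the 92% non-inferiority power statement need rewriting because it names no outcome, unit, visit, test arm or reference arm?

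*Combined protocol and SAP*

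**What the plan says.** The combined protocol and SAP contains one hypothesis test and one power figure, both in the sample size bullet of section 4: "Group sample sizes of 20 and 20 achieve 92% power to detect non-inferiority using a one-sided, two-sample t-test". The bullet goes on: "The margin of non-inferiority is -1.0", an assumed true difference of 0.1, alpha of 0.025, and "The data are drawn from populations with standard deviations of 1.0 and 1.0". It gives no outcome, unit or visit, and does not say which technique is the test arm.

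The clinical and esthetic outcomes listed just above it are on different scales. They include "Percentage previously visible root surface that has been covered by gingiva at 6- and 12-months following grafting" and "KT width as measured in mm by practitioner at 6- and 12-month following grafting", along with change in tissue thickness and the pink esthetic score. Each is assessed at 6 and 12 months, and none is labelled primary. The next bullet says that patient-centered outcomes could not be sized and that "in this respect this study serves as a pilot study".

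Section 3 (Study Background) gives the purpose as "to determine if there are any notable differences in post-operative healing and clinical outcomes associated with each technique". The title describes the study as a trial "to treat teeth with gingival recession and lack of adequate keratinized tissue. A pilot study".

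**The concern.** A non-inferiority margin has meaning only on a named scale and in a named direction. One margin of -1.0 and one SD of 1.0 cannot describe percent root coverage, millimetres of keratinized tissue and an esthetic score together, so the 92% cannot be read as power for the clinical outcomes in general.

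The direction raises a sharper worry. On the plan's inputs the 95% confidence interval is narrower on each side than the margin. At least one of the two possible claims (VISTA non-inferior to sulcular tunnel, or the reverse) will therefore nearly always succeed, which makes the test look as if it cannot fail until an arm is named.

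Finally, the background asks about differences in either direction, while the only test is one-sided. If these points carried through, a claim backed by 92% power could be chosen after the results were seen.

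**Working it through.** **Inputs (section 4, sample size bullet).** n = 20 per arm, margin -1.0, true difference 0.1, SD 1.0 in each arm, one-sided alpha 0.025.

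**1. The plan's own figure.**
- Standard error = 1.0 × √(2/20) = 0.3162, with df = 20 + 20 − 2 = 38.
- Noncentrality = (0.1 + 1.0) / 0.3162 = 3.479, with critical t(0.975, 38) = 2.024.
- Power from the noncentral t distribution = 0.9236, or 92.4%. The stated 92% reproduces, and 20 is the smallest n per arm that reaches it.

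**2. Which way the 0.1 points.** The same formula with other true differences (test minus reference):

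| True difference | Noncentrality | Power | n per arm for 92% |
|---|---|---|---|
| +0.1 | 1.1 / 0.3162 = 3.479 | 92.4% | 20 |
| 0 | 1.0 / 0.3162 = 3.162 | 86.9% | 24 |
| −0.1 | 0.9 / 0.3162 = 2.846 | 79.2% | 29 |

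The stated figure therefore implies that the 0.1 favours the test arm.

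**3. Scale.** Margin −1.0 and difference +0.1 are kept. The SDs other than 1.0 are assumptions, since the documents give none.

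| SD | Power |
|---|---|
| 1.0 | 92.4% |
| 1.5 | 61.8% |
| 2 | 39.6% |
| 10 | 5.3% |

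The 92% belongs to an outcome with an SD near 1.0. The row at 10 treats the margin as one percentage point of root coverage, and nothing shows that this was intended.

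**4. Direction left open.** Let D be the observed difference, VISTA minus sulcular tunnel.
- Half-width of the 95% CI at SD 1.0: h = 2.024 × 0.3162 = 0.640.
- VISTA passes if D > −1.0 + 0.640 = −0.360. Sulcular tunnel passes if D < 0.360.
- At least one is certain to pass when the pooled SD is below 1/0.640 = 1.562. With a true SD of 1.0 this has probability 0.999998.
- At zero true difference each direction passes in 86.9% of trials. Both pass in 2 × 0.869 − 1 = 0.738, about 74%, so only one passes in about 26%.

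These are pass rates. To see whether any of the passes are errors, compare the two null hypotheses: a true difference of −1.0 or less, and a true difference of +1.0 or more. They cannot both be true, so at most one of the two claims can be false. Simulating 1,000,000 trials with a true difference of −1.0, the false claim (VISTA non-inferior) passes in 2.5% even when both directions are tried. The other claim passes in nearly 100%, and it is true. At zero difference both claims are true on the plan's margin, so the 26% is a choice between true statements.

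**5. Does one direction always pass?** Only when the SD is near 1.0. At zero true difference and margin 1.0, at least one direction passes in 96% of trials at SD 1.5, 67% at SD 2 and 10% at SD 10 (assumed SDs).

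**The case for a change.** The strongest case for a change is that nothing else in the document fills the gap. The bullet is complete as printed, with no sign of redaction. The pilot wording inside section 4 covers only patient-centered outcomes, so the 92% is offered as real power for something clinical. Millimetres of keratinized tissue would fit a margin and SD of 1.0, but that is a guess, and it would still leave the visit and the test arm open. Writing these down would be cheap.

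Much of this stands. The omission is real, and a reader cannot apply the 92% to any particular outcome with certainty. The 2.5% bound is also per outcome and visit: it does not cover choosing the most favourable outcome or visit once results are known.

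What does not stand is the step from omission to a faulty analysis. The claim that the test cannot fail mistakes high power for error and depends on an SD near 1.0. The mismatch with the background aim is weak, because that sentence is general wording, and a one-sided test can sit beside an estimate with a two-sided interval. A two-sided 0.05 test with 20 per arm has only 34% power at 0.5 SD, but the plan proposes no such test. A request to name the outcome and arms cannot say which ones, because the documents do not supply them, and interval estimates for the remaining comparisons are routine reporting that corrects no stated analysis.

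**Conclusion.** No change to the plan follows. The power statement is arithmetically correct at 92.4%, and what is missing is a label that the investigators can supply and analysts would need before applying the margin at all. Leaving the arms unnamed does not raise the false non-inferiority rate above 2.5% for a given outcome and visit.

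The omission matters when reading the results. The 92% should be taken as power for one clinical outcome with an SD of about 1.0, measured on a scale where a deficit of 1.0 is tolerable, with the assumed 0.1 in favour of the test arm. With no true difference it is 86.9%, and with 0.1 against the test arm 79.2%. It should not be carried over to outcomes with a larger SD; at an assumed SD of 1.5 it would be 61.8%.

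This conclusion assumes the plan's SD of 1.0, 20 analysed patients per arm with one value each, and a single outcome and visit behind any non-inferiority claim.
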